13.1.2 EYE DRYNESS SCORE ON VISUAL ANALOG SCALE (EDS-VAS)

EDS-VAS CFB to Day 57 will be analyzed as described above for the analysis of CCSS with adjustment for baseline EDS-VAS instead of CCSS. Estimand 2 will be used for the analysis of EDS-VAS in the presence of an imbalance of missing data between the two treatment groups ([Section 2.6](#)).

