TITLE OF STUDY: A Phase 3, Multicenter, Randomized, Double-Masked and Placebo-Controlled Study Evaluating the Efficacy and Safety of Tanfanercept (HL036) Ophthalmic Solution 0.25% Compared to Placebo in Subjects with Dry Eye Disease (VELOS-3)	
PROTOCOL NUMBER: HL036-DED-US-P302	
STUDY SITES:	Multicenter study involving up to 10 sites located in the United States
STUDY PERIOD: Approximately 70 days	PHASE OF DEVELOPMENT: Phase 3
Investigational Product:	Tanfanercept ophthalmic solution 0.25%Placebo ophthalmic solution
STUDY OBJECTIVES: The objective of this study is to compare the safety and efficacy of tanfanercept ophthalmic solution 0.25% to placebo for the treatment of the signs and symptoms of dry eye.	
DOSE, ROUTE AND REGIMEN: Screening: During the 14-day (\pm 2 days) run-in period, open-label placebo ocular drops will be self-administered twice daily (BID) in both eyes in the morning and in the evening by all subjects. Treatment: Sterile active drug and placebo solutions are packaged into single-use 0.6 mL low density polyethylene (LDPE) unit dose ampoules that deliver an approximate per drop volume of 30 μ L. During the 8-week (57 \pm 3 days) treatment period, subjects will be instructed to self-administer one drop of tanfanercept ophthalmic solution 0.25% or placebo ophthalmic solution BID in each eye in the morning and the evening during the study period. Subjects will be randomized to one of two treatment arms (1:1) to receive study drug self-administered by subject at Visit 2.	
DURATION OF TREATMENT: Approximately 56 days (8 weeks)	
REFERENCE THERAPY, DOSE, ROUTE AND REGIMEN: Open-label placebo ophthalmic solution (placebo) will be provided to subjects from Day -14 to Day -1. Placebo ocular drops will be self-administered BID in both eyes in the morning and the evening. Following randomization, placebo will be dosed according to the same schedule as the tanfanercept ophthalmic solution 0.25%.	

NAME OF COMPANY	NAME OF DRUG PRODUCT
HanAll Pharmaceutical International Inc. [name] HanAll Biopharma, Co., Ltd. [name]	Tanfanercept ophthalmic solution 0.25% for treatment of Dry Eye Disease
NUMBER OF SUBJECTS PLANNED: Approximately 300 subjects will be enrolled in the study. The total number of expected participants, including screen failures, is approximately 857 subjects.	
INCLUSION CRITERIA:	

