8.4.1 Visit 1: Day -14 ± 2 – Screening

All subjects will undergo the following screening assessments:

- Informed Consent/HIPAA Prior to any changes in a subject's medical treatment and/or invasive procedures, the study will be discussed with each subject and subjects wishing to participate must give written informed consent and sign a HIPAA form.
- Medical / Medication History and Demographics Collect and record all demographic data, medical history, any medications and any underlying condition(s). Significant non-ocular medical history only within the past year and medications within the past 30 days will be captured. Record any medications the subject is taking, as well as those the subject may have taken but discontinued within 30 days prior to screening.
- Review of Inclusion and Exclusion Criteria
- Urine Pregnancy Test (for females of childbearing potential) Women of childbearing potential must have a negative urine pregnancy test to continue in the study.
- Ora Calibra® Ocular Discomfort Scale
- Ora Calibra® Ocular Discomfort & 4-Symptom Questionnaire
- Visual Analog Scale (VAS)
- OSDI®
- BCVA Utilizing an Early Treatment of Diabetic Retinopathy Study (ETDRS) Chart Subjects must have a score of [REDACTED] logMAR or better (Snellen equivalent score of [REDACTED]) in each eye at Visit 1.
- Slit-Lamp Biomicroscopy A slit-lamp exam will be performed at the beginning of the visit to exclude subjects with disallowed ocular conditions.
- Conjunctival Redness Score An objective measure used to score redness on the Ora Calibra® Conjunctival Redness Scale for Dry Eye. [REDACTED]
[REDACTED]
- Tear film break-up time (TFBUT)
- Corneal and Conjunctival Staining (fluorescein) as assessed by the Ora Calibra® Corneal and Conjunctival Staining Scale for Grading of Fluorescein Staining
- Corneal and Conjunctival Staining (lissamine green) as assessed by the Ora Calibra® Corneal and Conjunctival Staining Scale for Grading of Lissamine Green Staining
- Schirmer's Test
- IOP

- Dilated Fundus Exam
- Review of Inclusion and Exclusion Criteria
 - Report a score of █ according to the Ora Calibra® Ocular Discomfort & 4-Symptom Questionnaire in at least one of the dry eye symptoms at Visits 1
 - *Eligible subjects must have a positive response in at least one eye. A positive response is defined as meeting ALL of the following criteria in the same eye:*
 - Have a Schirmer's Test score of \leq 10 mm and \geq 1m in at least one eye at Visits 1

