- Note: If only one eye qualifies then the single qualifying eye will be the study eye. In the case that both eyes are eligible for analysis, the study eye will be the eye with worse (higher) central corneal fluorescein staining at Visit 2. If the central corneal fluorescein staining is the equivalent in both eyes, then the right eye will be selected as the study eye.
- **Randomization** – subjects will be randomized according to the following two strata:
 1. Visit 2 study eye CCSS █ and
 2. Visit 1 CCSS minus Visit 2 CCSS (V1 CCSS - V2 CCSS); difference in study eye CCSS █
- **Blood Sampling** Blood samples will be collected from all subjects for immunogenicity testing █

- Study Drug Instillation at the Study Site All subjects meeting all other screening eligibility criteria after Visit 2 will be randomized to one of two treatment arms. Randomized subjects will self-administer their initial study drug dose bilaterally at the study site.
- Ora Calibra® Drop Comfort Assessments The Ora Calibra® Drop Comfort Scale will be performed immediately after instillation and then at 1, 2, and 3 minutes following instillation.
- Monitoring and Query of AEs
- Study Drug Dispensation Prior to discharge from the study site on Visit 2 (Day 1), randomized subjects will be educated in the self-administration of study drug. The initial, self-administered dose taken in-office at Visit 2 will be counted as a morning dose regardless of visit time, and subjects will be instructed to administer an evening dose that night. Subjects will receive their assigned study drug kit with sufficient supply to last until Visit 3 and will be instructed NOT to self-administer study drug on the morning of their next scheduled study visit (Visit 3, Day 8).
- Schedule Next Visit Subjects will be scheduled for Visit 3.

8.4.4 Visit 3: Day 8 ± 1 –Week 1

- Study Drug Collection All used/unused study drug vials dispensed for Days 1 to 8 should be collected and reviewed by a trained study technician.
- Site staff must confirm that subjects have NOT administered their morning study drug dose at home. If subject dosed prior to the visit, study visit procedures should begin 4 hours after time of dosing.
- Monitoring and Query AEs
- Recording of all Changes in Concomitant Medications
- Ora Calibra® Ocular Discomfort Scale
- Ora Calibra® Ocular Discomfort & 4-Symptom Questionnaire
- VAS
- OSDI[©]
- BCVA Utilizing an ETDRS Chart
- Slit-Lamp Biomicroscopy
- Conjunctival Redness
- TFBUT

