If site is retained in the final primary analyses, the site by treatment interaction will be explored in a separate analysis to evaluate how the treatment effect may differ across sites. All post-baseline visits will be used in the model. Two-sample t-tests will also be conducted as supportive analyses.

Change from baseline of EDS from VAS at Day 57 ± 3 (V6, Week 8) between tanfanercept ophthalmic solution 0.25% and placebo will be analyzed as described for CFB of CCSS with adjustment for baseline EDS instead of baseline CCSS.

Example SAS code for the MMRM of the primary analyses is as follows:

```
PROC MIXED DATA = INDATA METHOD = REML;  
  CLASS SUBJID TREATMENT VISIT SITE;  
  MODEL CHG = BASELINE SITE VISIT|TREATMENT / DDFM = KR SOLUTION COVB;  
  REPEATED VISIT/SUBJECT = SUBJID TYPE = UN R RCORR;  
  LSMEANS TREATMENT TREATMENT*VISIT / CL PDIFF;  
RUN;
```

where

- *SUBJID* is the subject ID
- *TREATMENT* is the name of the treatment group variable
- *VISIT* is the visit
- *SITE* is the site id
- *CHG* is the change from baseline
- *BASELINE* is the baseline value

An alternate MMRM will be executed as a sensitivity analyses for both primary endpoints. These additional models will include all terms in the final models of the primary analyses.

Additional exploratory comparisons of the mean absolute scores of the primary endpoints at both Day 57 ± 3 (V6, Week 8) and baseline (V2) between the treatment groups will be conducted using two-sample t-tests and MMRM.

Least squares means and standard errors for each treatment group and for the difference between treatment groups will be presented from the MMRM together with two-sided p-values and 95% confidence intervals. Two-sided exact p-values and 95% confidence intervals will be presented from the permutation test with trimmed means.

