8.3 Definition of Baseline

Baseline measures are defined as the last measure prior to the initiation of study treatment, usually at Day 1.

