13.1 Primary Analyses

The primary efficacy endpoints of this study include mean CFB to Day 57 of central corneal staining score (CCSS) and eye dryness score on Visual Analog Scale (EDS-VAS).

CCSS will be graded using the Ora Calibra® Corneal and Conjunctival Fluorescein Staining Scale. The Ora Calibra® Corneal and Conjunctival Staining Scale ranges from [REDACTED]

EDS will be subjectively graded by the subjects using the VAS at all scheduled visits. Subjects are asked to rate each ocular symptom due to ocular dryness by placing a vertical mark on the horizontal line to indicate the current level of discomfort. 0% corresponds to “no discomfort” and 100% corresponds to “maximal discomfort.”

For both endpoints, CFB to each post-baseline protocol visit ([Section 3.1](#)) will be calculated using actual scores and resulting scores from multiple imputation methodology specified in Estimand 1 ([Section 2.6](#)). The imputation methods will be performed using the SAS® procedure PROC MI. Refer to [Appendix 1](#) for examples of SAS® codes for obtaining randomized treatment group-based MCMC multiple imputation data.

CFB to a post-baseline visit timepoint will be calculated as Post-baseline visit result minus Baseline visit results

Note: Positive difference indicates a worsening of dry eye signs or symptoms. In addition, treatment comparisons between active and placebo will be calculated as Active minus Placebo, such that a negative result indicates a better score for the active treatment (i.e., tafanercept group demonstrated less severity in dry eye signs or symptoms than the placebo group).

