13.1.1 CENTRAL CORNEAL STAINING SCORE (CCSS)

CCSS CFB to Day 57 will be analyzed using the ITT population with multiple imputation methodology specified in Estimand 1 ([Section 2.6](#)). The initial MMRM model will include terms for baseline CCSS, site, visit (as categorical term), treatment group and the interaction of treatment group and visit as fixed effects with correlated errors. The inclusion of site in the final model will be evaluated at an alpha level of 0.1. All post-baseline visits will be used in the model.

If site is retained in the final primary analyses, the site by treatment interaction will be explored in a separate analysis to evaluate how the treatment effect may differ across sites. All post-baseline visits will be used in the model.

An alternate MMRM will be executed as supportive analysis. This additional model will include all terms in the final model of the primary analyses with, [REDACTED]

Sensitivity analyses to compare CCSS CFB between treatment groups using imputation by Last Observation Carried Forward (LOCF), multiple imputation by placebo group-based pattern mixture models (PMM), and analyses of observed data only using the ITT and PP populations will be conducted.

The Least Square (LS) means, LS mean difference, Standard Errors (SEs), two-sided 95% CIs, and p-values of the LS mean difference will be reported from the MMRM model. Two-sample t-tests will also be conducted as supportive analyses of the mean CFB to Day 57. The sample means, sample mean difference, SEs, two-sided 95% CIs, and two-sided p-values will be reported from the two-sample t-test.

The MMRM LS means of the CCSS CFB in the study eye at Day 57 and CCSS CFB at each visit will be displayed graphically in a bar chart with SE bars by treatment group.

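### The primary EDS model is valid but adjusts only for the Visit 2 score; adding the Visit 1 EDS already collected before randomisation would probably gain some precision, by an unknown amount.

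*SAP*

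**What the plan says.** - **Primary EDS model.** SAP 13.1.2 carries over the CCSS analysis "with adjustment for baseline EDS-VAS instead of CCSS". Protocol 10.4.5 agrees: "with adjustment for baseline EDS instead of baseline CCSS".
- **Terms carried over.** SAP 13.1.1: "The initial MMRM model will include terms for baseline CCSS, site, visit (as categorical term), treatment group and the interaction of treatment group and visit". Site stays only if it passes a 0.1 test.
- **Baseline.** SAP 8.3: "Baseline measures are defined as the last measure prior to the initiation of study treatment, usually at Day 1". This is one value per subject.
- **When EDS is measured.** SAP 13.1: "EDS will be subjectively graded by the subjects using the VAS at all scheduled visits". Visit 1 is a scheduled visit in SAP Table 1. Protocol 8.4.1 and the visit schedules in both documents (Protocol Appendix 1, SAP Appendix 2) list the VAS at Visit 1 as well as Visit 2. Randomisation takes place at the end of Visit 2.
- **Imputation.** The SAP Appendix 1 code, written for CCSS, uses baseline and Visits 3 to 6. No Visit 1 score appears.
- **Estimand 2.** SAP 2.6 ranks subjects for trimming by outcome minus a slope times one baseline value.
- **Power.** The protocol synopsis says that the study is powered on the sign endpoint. SAP 5 repeats the power calculation at 260 randomised subjects, for CCSS only. Neither document gives an effect size, SD or power for EDS.

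**The concern.** EDS is a single self-rated mark of how the eyes feel at that moment, so one pre-treatment mark is a noisy measure of a subject's usual level. A second mark taken before randomisation may predict the Day 57 score beyond what the first does. If it does, leaving it out makes the standard error of the treatment difference larger than it need be.

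This matters more for EDS than for CCSS. CCSS has a stated power of 98.7% even at the reduced sample size. EDS is also a primary endpoint, tested second at two-sided 0.05, and its margin is not stated. The plan already treats Visit 1 information as relevant for the sign, since the change in CCSS from Visit 1 to Visit 2 is a randomisation stratum (Protocol 8.4.3). Nothing comparable is done for the symptom.

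**Working it through.** **1. The plan's own power figure (CCSS).** The difference and SD are redacted, so their ratio is solved from 99.4% power at 135 per arm, two-sided 0.05:

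d = (1.960 + 2.512) × √(2/135) = 0.544.

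At 119 per arm this gives 98.7%, as SAP 5 states. With 10% dropout, 260 × 0.9 / 2 = 117 rather than 119; power at 117 is 98.6%, so the difference is immaterial. There is no EDS figure to reproduce.

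**2. Formula for the gain.** Let a = corr(V1, V2), b = corr(V2, V6) and c = corr(V1, V6) for EDS. With V2 in the model, change from V2 and the V6 score give the same treatment comparison. The proportional fall in residual variance from adding V1 is the squared partial correlation of V6 with V1 given V2:

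(c − ab)² / [(1 − a²)(1 − b²)].

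This is the large-sample result for a Day 57 covariance analysis with complete data. The planned model uses one baseline slope for all visits, so the figures are approximations. Every correlation below is an assumption.

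**3. Equal correlations (a = b = c = r).** The formula reduces to [r/(1 + r)]².

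| r | Fall in variance | Fall in SE | 117 per arm acts like |
|---|---|---|---|
| 0.3 | 5.3% | 2.7% | 124 |
| 0.4 | 8.2% | 4.2% | 127 |
| 0.5 | 11.1% | 5.7% | 132 |
| 0.6 | 14.1% | 7.3% | 136 |
| 0.7 | 17.0% | 8.9% | 141 |

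**4. Correlation decaying with time.** Take a from 0.60 to 0.70, b from 0.50 to 0.60 and c from 0.40 to 0.55, with c no larger than b.

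| a / b / c | Calculation | Fall in variance |
|---|---|---|
| 0.70 / 0.60 / 0.42 | (0.42 − 0.42)² / (0.51 × 0.64) | 0% |
| 0.60 / 0.50 / 0.40 | 0.10² / (0.64 × 0.75) | 2.1% |
| 0.70 / 0.60 / 0.55 | 0.13² / (0.51 × 0.64) | 5.2% |
| 0.60 / 0.50 / 0.50 | 0.20² / (0.64 × 0.75) | 8.3% |
| 0.60 / 0.55 / 0.55 | 0.22² / (0.64 × 0.6975) | 10.8% |

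The gain is nil whenever c = ab, that is, when Visit 1 predicts Day 57 only through Visit 2. Values of c above b would give more (0.60 / 0.50 / 0.55 gives 0.25²/0.48 = 13.0%), but they make the earlier reading the better predictor, so they are left out of the range.

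**5. What this means for power.** Suppose EDS power with Visit 2 alone were 80% (assumed). A fall in variance of 11.1% raises it to 84.4%, and one of 17.0% to 86.7%. In the decay cases, 10.8% gives Φ[(1.960 + 0.842)/√0.892 − 1.960] ≈ 84%, and 0% leaves it at 80%.

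**6. Cost if Visit 1 adds nothing.** One degree of freedom among about 2 × 117 = 234 evaluable subjects, so a loss of roughly 1/234 = 0.4% in variance.

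**The case against.** The strongest reply is that nothing here is an error. Adjusting for the last pre-treatment value is standard and consistent between protocol and SAP, and it keeps the type I error rate. That stands. A reader might infer that the EDS comparison is biased or invalid; the documents give no support for that.

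A reader might also take the 11% to 17% gain as established, or say that the EDS confidence interval is certainly wider than the data allow. Neither can be shown. Equal correlation treats Visit 1 as interchangeable with Visit 2. Yet Visit 1 precedes a 14-day run-in on open-label placebo drops twice daily, while Visits 2 and 6 both follow regular dosing with study drops. Visit 1 is also further from Day 57 (14 + 56 = 70 days against 56). Some decay is the natural expectation, and a gain of zero lies inside the decay range.

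The consequence is limited as well. Success on CCSS alone makes the study a success, and EDS is tested only after it. One covariate does not make up for the absence of an EDS power calculation, which is a separate matter.

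Finally, the supportive alternate model for both primary endpoints contains a redacted term, so it cannot be said that Visit 1 data go unused throughout the plan. That model is supportive or a sensitivity analysis, and the primary EDS test is unaffected by it.

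What remains is that the score precedes randomisation, is scheduled for every subject, and costs almost nothing to include.

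**Conclusion.** The point holds as a low-cost efficiency improvement. The primary EDS model is valid but names only the Visit 2 EDS as an EDS covariate, and it probably gives up some precision on a primary endpoint with no stated power. Residual variance would fall by 11% to 17% under assumed equal correlations of 0.5 to 0.7, and by 0% to about 11% under the assumed decay pattern. The run-in makes the lower end plausible. Because Visit 1 precedes randomisation, adding it does not bias the comparison or change the difference in means being estimated.

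**What to change.** Before unmasking, amend the SAP as follows:

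- In 13.1.2, add Visit 1 EDS-VAS as a second covariate in the primary EDS model. Keep Visit 2 as the baseline from which change is calculated.
- In the EDS versions of the Appendix 1 imputation code (treatment-group MCMC and placebo-based pattern mixture), add the Visit 1 score to the variable lists and regression statements.
- In the Estimand 2 steps of SAP 2.6, fit the ANCOVA with both pre-randomisation scores and rank on the outcome minus both fitted slopes times their scores, so that trimming and the final model use the same covariates.

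The VAS, OSDI and ocular-discomfort secondary endpoints also have Visit 1 values. Extending the change to them is optional, because they are not type I error controlled and are hypothesis-generating.

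The cost is about one degree of freedom in the analysis model, and SAP wording and code. No new data are needed.

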13.2 Secondary Analyses

The following secondary efficacy endpoints will be tested:

- Fluorescein staining (Ora Calibra® scale) by region: central, superior, inferior, temporal, nasal, corneal sum, conjunctival sum, and total staining
- Lissamine green staining (Ora Calibra® scale) by region: central, superior, inferior, temporal, nasal, corneal sum, conjunctival sum, and total staining
- Conjunctival Redness
- Unanesthetized Schirmer's Test
- TFBUT
- VAS
- OSDI®
- Ora Calibra® Ocular Discomfort Scale
- Ora Calibra® Ocular Discomfort & 4-Symptom Questionnaire

- Ora Calibra® Drop Comfort assessment

13.2.1 ANALYSES OF SECONDARY ENDPOINTS

Actual scores will be summarized by visit and region/symptom using quantitative summary statistics. Two-sample t-tests will be employed to compare active treatment and placebo means of actual scores at each visit. The differences in samples means, SEs, two-sided 95% CIs for the difference in means and p-values will be reported.

Changes from baseline at each post-baseline visit will be summarized similarly. Analysis of the change from baseline at each post-baseline visit will utilize MMRM models similar to the primary analysis (substituting appropriate baseline and week variables) using observed data. The LS means, LS mean differences, SEs, two-sided 95% CIs for the difference in means and two-sided p-values will be reported from the models. Two sample t-tests will also be conducted. Within each treatment arm, paired t-tests will be conducted for changes from baseline. Analyses will be performed on the ITT population with observed data only. For assessments on both eyes, only the study eye will be analyzed and summarized.

Subject listings of each secondary efficacy assessment will be generated.

13.2.2 FLUORESCEIN STAINING

Corneal and conjunctival fluorescein staining will be performed at all scheduled visits, on both eyes and graded using the Ora Calibra® Corneal and Conjunctival Staining Scale. The scale will grade the cornea and conjunctiva by five regions: inferior, superior, central, temporal, and nasal. The Ora Calibra® Corneal and Conjunctival Staining Scale ranges from [REDACTED]

[REDACTED] The corneal sum score will be the sum of scores from the inferior, superior, and central regions. The conjunctival sum score will be the sum of scores from the nasal and temporal regions. The total eye score will be the sum of scores from all five regions.

Fluorescein staining scores will be summarized and analyzed by visit and region including sums as described in [section 13.2.1](#).

Sample means of the fluorescein staining scores in the study eye will be displayed graphically in a line chart with SE bars by visit and treatment group for each region or sum separately.

13.2.3 LISSAMINE GREEN STAINING

Corneal and conjunctival lissamine green staining will be performed at all visits, on both eyes and graded using the Ora Calibra® Corneal and Conjunctival Staining Scale. The scale will grade the cornea and conjunctiva by five regions: inferior, superior, central, temporal, and nasal. The Ora Calibra® Corneal and Conjunctival Staining Scale ranges from [REDACTED]

[REDACTED] The corneal sum score will be the sum of scores

from the inferior, superior, and central regions. The conjunctival sum score will be the sum of scores from the nasal and temporal regions. The total score will be the sum of scores from all five regions.

Lissamine green staining scores will be summarized and analyzed by visit and region including sums as described in [section 13.2.1](#).

Sample means of the lissamine green staining scores in the study eye will be displayed graphically in a line chart with SE bars by visit and treatment group for each region or sum separately.

